3.4.2 Secondary Efficacy Endpoints

Similar ANCOVA models as described for the primary analyses will be used to analyze the secondary efficacy endpoints and will be tested sequentially at the 0.05 significant level according to the order specified below, if all 3 co-primary endpoints achieved statistical significance. Otherwise, all statistical comparisons for secondary endpoints are considered descriptive only:

- Percent change from Day 1 to Day 84 in non-HDL-C for the obicetrapib 10 mg + ezetimibe 10 mg FDC treatment group compared with the placebo group;
- Percent change from Day 1 to Day 84 in ApoB for the obicetrapib 10 mg + ezetimibe 10 mg FDC treatment group compared with the placebo group;
- Percent change from Day 1 to Day 84 in non-HDL-C for the obicetrapib 10 mg monotherapy treatment group compared with the placebo group;
- Percent change from Day 1 to Day 84 in ApoB for the obicetrapib 10 mg monotherapy compared with the placebo group;

- Percent change from Day 1 to Day 84 in non-HDL-C for the obicetrapib 10 mg + ezetimibe 10 mg FDC treatment group compared with the ezetimibe 10 mg monotherapy treatment group;
- Percent change from Day 1 to Day 84 in ApoB for the obicetrapib 10 mg + ezetimibe 10 mg FDC treatment group compared with the ezetimibe 10 mg monotherapy treatment group;
- Percent change from Day 1 to Day 84 in non-HDL-C for the obicetrapib 10 mg + ezetimibe 10 mg FDC treatment group compared with the obicetrapib 10 mg monotherapy treatment group; and
- Percent change from Day 1 to Day 84 in ApoB for the obicetrapib 10 mg + ezetimibe 10 mg FDC treatment group compared with the obicetrapib 10 mg monotherapy treatment group.

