9.2.1.1 Primary efficacy analysis

The primary efficacy endpoint is the percent change from Day 1 to Day 84 in LDL-C. Co-primary endpoints include the percent change from Day 1 to Day 84 in LDL-C for the obicetrapib 10 mg + ezetimibe 10 mg FDC treatment group compared with each of the following: placebo, ezetimibe 10 mg monotherapy, and obicetrapib 10 mg monotherapy, and for the obicetrapib 10 mg monotherapy treatment group compared with placebo. The primary endpoint

will be analyzed using an analysis of covariance (ANCOVA) model with a fixed effect for the treatment group and a covariate of baseline LDL-C. The least squares (LS) mean, standard errors, and 2-sided 95% confidence intervals for each treatment group and for the mean difference compared to placebo will be obtained.

Each of the comparisons within the co-primary endpoint family will be conducted at a significance level of 0.05. If and only if all 4 testing achieve statistical significance, the study is claimed to meet its primary objective and the hypothesis testing will continue to secondary endpoints, otherwise all statistical comparisons for secondary endpoints are considered descriptive only.

The primary estimand will correspond to a treatment policy estimand. The target population will comprise participants who are randomized into the study. The primary summary measure to assess the treatment effect will be the LS mean difference for the primary endpoint between obicetrapib 10 mg + ezetimibe 10 mg FDC treatment and placebo, ezetimibe 10 mg monotherapy, and obicetrapib 10 mg monotherapy based on the ANCOVA methodology. The primary estimand will be addressed using the in-study observation period (ie, including data collected post treatment discontinuation or post prohibited medication use).

Missing data will be imputed for the primary efficacy analysis based on a pattern mixture model that uses a multiple imputation technique analyzed with ANCOVA with pre-specified fixed factors and covariates. If appropriate, based on the number of retrieved dropouts, missing measurements of non-retrieved dropouts will be modeled by known measurements from retrieved dropouts (ie, participants who remain in the study after treatment discontinuation) in the same treatment group. The imputation model will be further clarified in the SAP.

Additional sensitivity analyses may be carried out under secondary estimands and/or various assumptions for missing data. Full details will be provided in the SAP.

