9.2.1.2 Secondary efficacy analyses

In order to control the Type I error rate, a fixed sequential testing procedure will be implemented. In a hierarchical step-down manner, the co-primary endpoints will be tested first, followed by the secondary efficacy endpoints in the order specified. Continuous secondary efficacy endpoints will be analyzed using similar methods as in the primary efficacy analysis.

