3.1.5 Hypothesis Testing

The percentage change in LDL-C from Baseline to Day 84 for each treatment group is defined mathematically as μ_j , where j stands for the jth treatment (j=0,1,2,3) and the subscript 0 refers to the placebo, 1 refers to obicetrapib 10 mg monotherapy, 2 refers to ezetimibe 10 mg monotherapy, and 3 refers to the FDC treatment group. The hypothesis testing to the percent change in LDL-C from Baseline to Day 84 is then defined statistically as following:

$$H_0$$
: μ_3 - μ_j = 0 (where j=0,1,2) and μ_1 - μ_0 = 0

$$H_1$$
: μ_3 - $\mu_i \neq 0$ (where j=0,1,2) and μ_1 - $\mu_0 \neq 0$.

Each of the comparisons within the co-primary endpoint family will be conducted at a significance level of 0.05. If and only if all 4 testing achieve statistical significance, the study is claimed to meet its primary objective and the hypothesis testing will continue to secondary endpoints, otherwise all statistical comparisons for secondary endpoints are considered descriptive only.

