3.4.1 Primary Efficacy Endpoints

Primary Analysis

The primary efficacy endpoint is the percent change from Day 1 to Day 84 in LDL-C. Co-primary endpoints include the percent change from Day 1 to Day 84 in LDL-C for the obicetrapib 10 mg + ezetimibe 10 mg FDC treatment group compared with each of the following: placebo, ezetimibe 10 mg monotherapy, and obicetrapib 10 mg monotherapy, and for the obicetrapib 10 mg monotherapy treatment group compared with placebo.

Each of the comparisons within the co-primary endpoint family will be conducted at a significance level of 0.05. If and only if all 4 testing achieve statistical significance, the study is claimed to meet its primary objective and the hypothesis testing will continue to secondary endpoints, otherwise all statistical comparisons for secondary endpoints are considered descriptive only.

The LDL-C values measured by preparative ultracentrifugation (PUC) will be used. If the later measurement is not available, the LDL-C values will be assumed missing.

All the analysis for primary efficacy endpoint will be repeated with LDL-C values calculated as follows:

- 1. LDL-C will be calculated using the Friedewald equation unless triglycerides ≥400 mg/dL or LDL-C ≤50 mg/dL; where, LDL-C level will be measured directly by PUC.
- 2. LDL-C will be calculated using the Martin-Hopkins equation unless triglycerides ≥400 mg/dL or LDL-C ≤50 mg/dL; where, LDL-C level will be measured directly by PUC.

Primary Estimand

To assess the primary efficacy endpoint, the primary estimand is defined by the following key attributes:

- **Treatment**: obicetrapib 10 mg + ezetimibe 10 mg FDC treatment versus placebo, ezetimibe 10 mg monotherapy, and obicetrapib 10 mg monotherapy, and obicetrapib 10 mg monotherapy versus placebo
- Target Population: participants who are randomized into the study
- **Analysis Population**: The ITT Population
- Intercurrent events: treatment discontinuation, prohibited medication use

- **Analysis set and handling of intercurrent events**: Treatment policy strategy will be used. All available values of LDL-C at Baseline and Day 84 will be included in the calculation of the percentage change from Baseline to Day 84.

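### SAP 3.4.2 opens the secondary tests after three co-primary successes, but the protocol and the rest of the SAP require four, and the three-test gate does not control Type I error

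*SAP*

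**What the plan says.** The co-primary family has four members throughout. Three compare the FDC with placebo, with ezetimibe and with obicetrapib; SAP 3.4.1 adds the fourth, "and for the obicetrapib 10 mg monotherapy treatment group compared with placebo". On level, SAP 3.1.5 states: "Each of the comparisons within the co-primary endpoint family will be conducted at a significance level of 0.05".

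Three sections give the same gate to the secondary tests:

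- Protocol 9.2.1.1: "If and only if all 4 testing achieve statistical significance", testing continues to the secondary endpoints; otherwise those comparisons are descriptive.
- SAP 3.4.1: "If and only if all 4 testing achieve statistical significance, the study is claimed to meet its primary objective", with the same consequence for the secondaries.
- SAP 3.1.5 repeats that rule.

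SAP 3.4.2 lists the eight secondary tests, which "will be tested sequentially at the 0.05 significant level according to the order specified below", but on a different condition: "if all 3 co-primary endpoints achieved statistical significance". It does not identify the three.

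Protocol 9.2.1.2 gives the purpose of the sequence: "In order to control the Type I error rate, a fixed sequential testing procedure will be implemented". SAP section 5 declares one change from the protocol, the inclusion of subgroup analysis.

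**The concern.** The two conditions cannot both be followed. Suppose the three FDC comparisons succeed and obicetrapib versus placebo fails on LDL-C. SAP 3.1.5 and 3.4.1 then make every secondary descriptive, while SAP 3.4.2 tests them at 0.05. The third and fourth secondary tests are obicetrapib versus placebo on non-HDL-C and ApoB, so a contrast that had just failed on LDL-C could support confirmatory claims on related lipids.

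A fixed sequence protects the error rate because a failed step stops testing. Protocol 9.2.1.2 relies on this: "In a hierarchical step-down manner, the co-primary endpoints will be tested first, followed by the secondary efficacy endpoints in the order specified". With a three-test gate, failure of the fourth co-primary stops nothing. The level of 0.05 is spent on that comparison and again on the first true null among the secondaries. If the conflict were settled after unblinding, the choice of rule would also depend on the data.

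**Working it through.** **Inputs.** Level 0.05 for each co-primary (SAP 3.1.5), two-sided because the alternative is inequality; 0.05 for each secondary (SAP 3.4.2). SAP 2.2.2 gives 95 evaluable per arm, SD 25 points, and differences of 30 (FDC–placebo), 20 (FDC–ezetimibe), 12 (FDC–obicetrapib) and 15 (obicetrapib–placebo). The documents give no correlation between the LDL-C and non-HDL-C tests; 0.70 to 0.95 is an assumed range, with 0 as a bound. The three comparisons in SAP 3.4.2 are read as the FDC ones.

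**1. The plan's own figures.** SE = 25 × √(2/95) = 3.627, and power = Φ(difference/SE − 1.96).

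| Difference | Power |
|---|---|
| 30 | >0.999 |
| 20 | 0.9998 |
| 12 | 0.911 |
| 15 | 0.985 |

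All exceed 90%, and 380/0.95 = 400. The stated figures reproduce.

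**2. How often each gate opens if the fourth null is true.** Take mean LDL-C changes of 0 (placebo), 0 (obicetrapib), −10 (ezetimibe) and −30 (FDC). In 200,000 simulated trials with 95 per arm, the three-test gate opens in 99.98% and the four-test gate in about 5.0%. In about 95% the three-test gate opens although the fourth co-primary failed.

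**3. Error under the three-test gate.** A false obicetrapib-versus-placebo claim has two routes: the fourth co-primary, and secondary test 3. The fourth secondary is reached only after the third rejects, so it adds no further error. For two two-sided tests the error is P(|Z₁| > 1.96 or |Z₂| > 1.96). At zero correlation this is 1 − 0.95² = 0.0975. The bivariate normal gives:

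| Correlation | Three-test gate |
|---|---|
| 0.95 | 0.0646 |
| 0.90 | 0.0704 |
| 0.80 | 0.0781 |
| 0.70 | 0.0835 |
| 0 | 0.0975 |

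Simulation with the non-HDL-C secondaries agrees: 0.065, 0.071 and 0.078 at correlations 0.95, 0.90 and 0.80. If the first true secondary null were instead FDC versus placebo on non-HDL-C, the simulated error is 0.091 to 0.099. Under the four-test gate it is 0.049 to 0.051 in every null configuration tried.

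**4. How often the gates disagree under the planning effects.** The four planned differences cannot all hold at once, since 15 + 12 = 27, not 30. The consistent subsets give:

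| FDC–placebo | FDC–obicetrapib | Obicetrapib–placebo | P(three pass) | P(four pass) | Gap |
|---|---|---|---|---|---|
| 27 | 12 | 15 | 0.911 | 0.896 | 1.5% |
| 30 | 15 | 15 | 0.985 | 0.970 | 1.5% |
| 30 | 12 | 18 | 0.911 | 0.910 | 0.1% |

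**5. How far the sequence would run.** In the scenario of step 2, the chance that secondary test 3 rejects after the fourth co-primary failed is (error − 0.05)/0.95. That is (0.0646 − 0.05)/0.95 = 1.5% at correlation 0.95 and (0.0835 − 0.05)/0.95 = 3.5% at 0.70.

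**The case against.** The intended rule is recoverable. Protocol 9.2.1.1, SAP 3.1.5 and SAP 3.4.1 each state the gate to the secondaries as an if-and-only-if on four tests, and SAP section 5 declares no relaxation. SAP 2.3.1 lists three FDC comparisons as bullets with the fourth in a trailing sentence, so the figure in 3.4.2 may be a miscount. This is a fair inference about intent, but it does not correct the section a programmer would follow for the secondary tests.

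The inflation also needs a particular state of nature: obicetrapib inert alone, yet the FDC better than ezetimibe. If the effects are additive, obicetrapib equal to placebo makes FDC equal to ezetimibe. A true null then sits inside the three-test gate, which opens in at most 5% of trials (4.9% in simulation, with an assumed ezetimibe effect of 18 points), and the error stays within 5%. Protocol 1.4 reports a 45.3% LDL-C reduction on obicetrapib 10 mg, which makes that null remote. This stands: the figures in step 3 are a worst case. Strong control, however, must cover that case.

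Lastly, step 5 shows that eight claims against none is the extreme. In the null scenario the sequence would usually stop after the two FDC-versus-placebo secondaries, so the typical conflict is two confirmatory claims against none. That also stands, and it remains a conflict.

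**Conclusion.** The concern holds. The contradiction is certain from the text and concerns the decision rule for every confirmatory secondary claim. Read as the three FDC comparisons, the SAP 3.4.2 gate raises the chance of a false obicetrapib-versus-placebo claim from 5% to between 6.5% and 8.3% over the assumed correlations of 0.95 to 0.70, and to 9.75% at zero correlation. This requires that the FDC beats all three comparators on LDL-C while obicetrapib alone equals placebo. A three-test gate could control error only if the fourth comparison left the confirmatory family, and the documents keep it there at the full 0.05.

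Under the planning effects the gates disagree in about 0.1% to 1.5% of trials, so the practical effect is probably small. The correction is still needed before unblinding, because the rule matters precisely when a co-primary fails.

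**What to change.** In SAP 3.4.2, make secondary testing conditional on significance of all 4 co-primary comparisons, and name them: FDC versus placebo, FDC versus ezetimibe, FDC versus obicetrapib, and obicetrapib versus placebo. This matches Protocol 9.2.1.1, SAP 3.1.5 and SAP 3.4.1. The cost is one phrase in the SAP before unblinding; the primary analysis and sample size do not change.

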3.4.3 Exploratory Efficacy Endpoints

Similar ANCOVA models as described for the primary analyses will be used to assess in obicetrapib 10 mg + ezetimibe 10 mg FDC treatment group compared with the placebo treatment group, ezetimibe 10 mg monotherapy treatment group, and obicetrapib 10 mg monotherapy treatment group, and obocetrapib 10 mg monotherapy treatment group compared with the placebo treatment group for the following:

- Percent change from Day 1 to Day 84 in VLDL-C, HDL-C, TG, Lp(a), and sdLDL-C
- Percent change from Day 1 to Day 84 in particle numbers and size, as measured by NMR analysis, of LDL-C, HDL-C, and VLDL-C
- Percent change from Day 1 to Day 28 in LDL-C.

For the percentage change from Day 1 to Day 28 in LDL-C, the LDL-C will be calculated using the Martin-Hopkins equation unless the Triglyceride value is ≥400 mg/dL or the LDL-C value is ≤50 mg/dL; in which case, the LDL-C level measured directly by PUC will be used in the analysis. The latter approach will be used because PUC assessments are not performed at Day 28 as per the protocol, unless the conditions for Triglycerides or LDL-C described above are met at the Day 28 assessment. The analysis will be repeated using the Friedewald equation as described in the Section Error! Reference source not found. above.

The proportion of participants at Days 84 who achieved

LDL-C levels of <55 mg/dL (<1.4 mmol/L), <70 mg/dL (1.8 mmol/L), and <100 mg/dL (<2.6 mmol/L)

in the obicetrapib 10 mg + ezetimibe 10 mg FDC treatment group compared with the placebo treatment group, ezetimibe 10 mg monotherapy treatment group, and the obicetrapib 10 mg monotherapy treatment group, and obicetrapib 10 mg monotherapy compared with the placebo treatment group will be examined using logistic regression models with covariates of treatment group and respective baseline values as covariates. Odds ratio with 95% confidence intervals will be estimated.

The logistic regression model will be implemented using SAS® Proc LOGISTIC. The sample SAS code can be found below:

3.4.4 Subgroup Analysis

The primary efficacy endpoint also may be analyzed by the following subgroups:

- Sex (male, female)
- HIS, non-HIS. HIS include atorvastatin 40 or 80 mg, rosuvastatin 20 or 40 mg. Participants will be defined as having HIS therapy based on the data collected in the eCRF and if any following were used at baseline: average daily dose of atorvastatin ≥40 mg or average daily dose of rosuvastatin of ≥20 mg. Participants having any other doses of statin or another statin or no statin will be defined as having non-HIS therapy;
- The history of ASCVD (Yes, No).

The ANCOVA model with a fixed effects for the treatment group, subgroup variable, treatment-by-subgroup variable and covariates of Baseline LDL-C will be used. The least squares (LS) mean, standard errors, and 2-sided 95% confidence intervals for each treatment group and for the mean difference compared to placebo, within each level of the subgroup, will be estimated. No imputation of missing data will be performed; therefore, the subgroup analysis will perform using only observed data. For the primary efficacy endpoint, the LDL-C values measured by preparative ultracentrifugation will be used. However, if the analysis for the primary efficacy endpoint specified above will show a difference between the 3 LDL-C approaches, then Friedewald and Martin-Hopkins equations may be considered for subgroup analysis.

3.5 Safety Assessment

Safety Population will be the primary population for the safety analyses. All safety endpoints will be summarized descriptively by treatment group and overall. No statistical inference will be applied to the safety endpoints.

3.5.1 Adverse Events (AEs)

AEs will be categorized by primary system organ class and preferred term as coded using the current MedDRA version category designation.

An overview of treatment-emergent AEs (TEAEs) will be provided including counts and percentages of participants with the following:

- Any TEAEs (overall and by maximum severity)
- Any TEAEs (non-serious)
- Any study drug related TEAEs (overall and by maximum severity)
- Any TEAEs leading to discontinuation of study drug
- Any drug related TEAEs leading to discontinuation of study drug
- Any treatment-emergent serious AEs (TESAEs)
- Any study drug related TESAEs
- Any TEAEs leading to death.

The TEAEs described above will be summarized separately by system organ class and preferred term. The non-serious TEAEs occurring in more than 2% of participants in any treatment group and preferred term will be summarized.

Listings will be presented specifically for TEAEs, TESAEs, TEAEs leading to discontinuation of study drug, and TEAEs leading to death.

3.5.2 Event of Special Interest

Events of special interest (ESIs) include the following: hepatic abnormalities, muscle-related abnormalities, new-onset diabetes mellitus (NODM) and/or hyperglycemia, renal abnormalities, changes to antihypertensive medication(s) due to changes in blood pressure, and macular degeneration described as follows:

- AST or ALT > 3×ULN;
- Total bilirubin > 2×ULN;
- Creatine kinase (CK) > 5 × ULN;
- NODM or worsening of glycemic control;

Note: NODM is defined by 1 or more of the following criteria, based upon information from AE, medication, and laboratory data:

- AE indicating new type 1 or type 2 diabetes;
- Initiation of anti-diabetes medication with confirmation of the diagnosis of diabetes by blinded external review by experts in diabetology;
- HbA1c ≥6.5% (≥0.065 hemoglobin fraction); and/or
- Two consecutive values of fasting plasma glucose that are ≥126 mg/dL (≥7.0 mmol/L).

Note: Worsening of glycemic control will be defined as HbA1c increase from baseline >0.5% (>0.005 hemoglobin fraction) and/or a new concomitant medication or increase in current antidiabetic therapy in a participant with a baseline HbA1c \ge 6.5% (\ge 0.065 hemoglobin fraction)

- A >25% decrease in eGFR from Baseline or an eGFR<30mL/min/1.73 m², calculated using the Chronic Kidney Disease Epidemiology Collaboration equation, and/or an increase in serum creatinine of ≥0.3 mg/dL (≥26.5 µmol/L) from baseline;
- Changes to antihypertensive medication(s) due to changes in blood pressure in those participants receiving antihypertensive medication(s) treatment at baseline, and new

antihypertensive medication prescriptions for participants not previously treated for hypertension; and

Macular degeneration.

Values and changes from baseline will be summarized for ALT, AST, and total bilirubin by visit and treatment group. The number and percent of participants with abnormal values for ALT, AST, and total bilirubin will be summarized. These summaries of participants with abnormal values will be performed overall; by normal Baseline; and by abnormal Baseline for ALT, AST, and total bilirubin individually.

Values and changes from baseline will be summarized for CK levels by visit and treatment group and visit. In addition, the number and percent of participants with abnormal CK values will be summarized. These summaries of participants with abnormal CK values will be performed overall, by normal Baseline CK, and by abnormal Baseline CK. Values of CK from Baseline to EOT will be summarized by treatment group and by Baseline eGFR category.

Cases of NODM will be recorded and summarized using the appropriate system organ class. These events will be summarized by severity and relationship to study drug for each treatment group.

Baseline eGFR will be summarized by treatment group for actual value and for baseline eGFR categories. Shift tables of eGFR category from baseline to EOT will be provided by treatment group. Shift tables of urine albumin-creatinine ratio from baseline to EOT will be provided by treatment group.

Participants will be identified as those who have a diagnosis of hypertension in their medical history and received antihypertensive medication(s) at Baseline. If a participant has an adverse event related to hypertension after Baseline (see Appendix B for preferred terms) and has any change in antihypertension medication within 30 days of the start date of the adverse event, that change in antihypertension medication will be considered due to a change in blood pressure. Participants will be identified as those who did not have a prior diagnosis of hypertension in their medical history but had an adverse event of hypertension (see Appendix B) after Baseline. If participants had an adverse event of hypertension and had initiation of antihypertension medication within 30 days of the start date of the adverse event, that initiation of an antihypertension medication will be considered due to a change in blood pressure.

The number and percentage of participants receiving/not receiving antihypertensive medication(s) at Baseline with changes to or initiation of new antihypertensive medication(s) due to changes in blood pressure will be summarized by treatment group.

Cases of macular degeneration will be recorded and summarized using the appropriate system organ class. These events will be summarized by severity and relationship to study drug for each treatment group.

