8.1.4 Events of Special Interest

ESIs will be monitored, regardless of whether these events were reported as AEs. Any events that qualify as an AE or SAE will be reported accordingly (see Sections 8.1, 8.2, and 8.3).

ESIs will include the following hepatic abnormalities, muscle-related abnormalities, new-onset diabetes mellitus (NODM) and/or hyperglycemia, renal abnormalities, changes to antihypertensive medication(s) due to changes in blood pressure, and ophthalmic events (ie, macular degeneration), described as follows:

- AST or ALT > 3 × ULN;
- Total bilirubin >2 × ULN;
- CK >5 × ULN;
- NODM or worsening of glycemic control;

Note: NODM is defined by 1 or more of the following criteria, based upon information from AE, medication, and laboratory data:

- o AE indicating new type 1 or type 2 diabetes;
- o Initiation of anti-diabetes medication with confirmation of the diagnosis of diabetes by blinded external review by experts in diabetology;

- o HbA1c \geq 6.5% (\geq 0.065 hemoglobin fraction); and/or
- Two consecutive values of fasting plasma glucose that are \geq 126 mg/dL (\geq 7.0 mmol/L).

Note: Worsening of glycemic control will be defined as an HbA1c increase from baseline >0.5% (>0.005 hemoglobin fraction) and/or a new concomitant medication or increase in current antidiabetic therapy in a participant with a baseline HbA1c $\ge 6.5\%$ (≥ 0.065 hemoglobin fraction).

- A >25% decrease in eGFR from baseline or an eGFR <15 mL/min/1.73 m², calculated using the Chronic Kidney Disease Epidemiology Collaboration equation, and/or an increase in serum creatinine of ≥0.3 mg/dL (≥26.5 μmol/L) from baseline;
- Changes to antihypertensive medication(s) due to changes in blood pressure in those
 participants receiving antihypertensive medication(s) treatment at baseline, and new
 antihypertensive medication prescriptions for participants not previously treated for
 hypertension; and
- Macular degeneration.

These ESIs will be monitored through review of the AE and laboratory databases.

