3.3.6 Concomitant Medications

The Prior & Concomitant Medications case report form where medication start and stop dates are recorded, will be used to determine whether the medications are prior or concomitant to the study treatment. Concomitant medications are defined as those used on or after the first dose of the study drug. Prior medications are defined as those used prior to and stopped before the first dose of study drug. All prior and concomitant medications will be coded using the current World Health Organization (WHO) Drug Dictionary. Counts and percentages of subjects taking prior and concomitant medications will be summarized by anatomical therapeutic chemical (ATC) class and preferred term by treatment group and overall, for the Safety Population.

Concomitant medications will be listed.

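### As worded, any new concomitant medication in a participant with baseline HbA1c of at least 6.5% meets the definition of worsening of glycemic control, because neither document limits that alternative to antidiabetic drugs

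*SAP*

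**What the plan says.** SAP Section 3.5.2 lists "NODM or worsening of glycemic control" among the events of special interest (ESIs). Its note on worsening gives an HbA1c increase from baseline above 0.5%, and/or "a new concomitant medication or increase in current antidiabetic therapy in a participant with a baseline HbA1c" of at least 6.5%. Protocol Section 8.1.4 has the same medication wording: "and/or a new concomitant medication or increase in current antidiabetic therapy in a participant with a baseline HbA1c" of at least 6.5%.

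SAP Section 3.3.6 gives the plan's meaning of the key term: "Concomitant medications are defined as those used on or after the first dose of the study drug". It names no drug class or indication. The same section plans ATC coding of all prior and concomitant medications.

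SAP Section 2.3.4 includes the incidence of ESIs in the safety endpoint. SAP Section 3.5 has all safety endpoints summarized descriptively, by treatment group and overall, without inference.

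**The concern.** The medication part of the definition has two alternatives, and only the second is tied to diabetes treatment. Take two participants with baseline HbA1c of 7.0%. One starts an antibiotic on Day 40, with no change in glucose, HbA1c or diabetes drugs. The other has a metformin dose increased. Under the text as written both are cases, although only the second shows worsening of glycemic control.

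At stake is how specific one descriptive safety category is. Unrelated prescriptions would be expected at broadly similar rates in every arm. Adding them raises the count everywhere and draws a ratio between arms toward 1, and in a safety summary that error is in the unhelpful direction.

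The medication part is still worth keeping. Under Protocol Section 8.7.1, HbA1c is measured only at Screening, Day 84 and an End of Treatment visit. Worsening that is treated between those visits, or after Day 84, may show only as a change in antidiabetic drugs.

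**Working it through.** The plan states no expected rate for this ESI, so there is no figure to reproduce. The check is of the text, followed by an illustration on assumed rates.

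**1. Grammar.** The alternatives are (a) a new concomitant medication and (b) an increase in current antidiabetic therapy. The adjective stands inside (b), after the *or*. Nothing in the sentence carries it back to (a).

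**2. Defined term.** Under SAP Section 3.3.6 a concomitant medication is defined by date of use alone. With that meaning, (a) takes in any newly started drug, including the COVID-19 treatments that Protocol Section 1.6.1 permits.

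**3. Search for a limit elsewhere.** Neither document gives an ATC class, an indication or an attribution rule for (a). Both carry the same words, so neither corrects the other.

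**4. Neighbouring criteria.** These do name their class:
- New-onset diabetes (NODM): "Initiation of anti-diabetes medication with confirmation of the diagnosis of diabetes by blinded external review by experts in diabetology".
- Antihypertensive changes: a participant with a hypertension-related adverse event qualifies if he or she "has any change in antihypertension medication within 30 days of the start date of the adverse event".

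**5. Path to output.** The only glycaemic ESI summary that SAP Section 3.5.2 describes is for NODM: "Cases of NODM will be recorded and summarized using the appropriate system organ class". No table is described for worsening. The definition still feeds ESI incidence, which Sections 2.3.4 and 3.5 require to be summarized.

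**6. Illustration only.** Let p_new be the probability that a participant with baseline HbA1c of at least 6.5% starts at least one unrelated drug, and p_true the rate of worsening under the intended meaning. If the two are independent, the literal rate is 1 − (1 − p_new)(1 − p_true). Assume p_new of 20% to 60%, and p_true of 5% in one arm and 10% in the other. None of these rates is in the documents.

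| p_new | Literal rate, p_true 5% | Literal rate, p_true 10% | Ratio | Difference |
|---|---|---|---|---|
| 0% (intended meaning) | 5% | 10% | 2.00 | 5 points |
| 20% | 1 − 0.80 × 0.95 = 24% | 1 − 0.80 × 0.90 = 28% | 1.17 | 4 points |
| 40% | 1 − 0.60 × 0.95 = 43% | 1 − 0.60 × 0.90 = 46% | 1.07 | 3 points |
| 60% | 1 − 0.40 × 0.95 = 62% | 1 − 0.40 × 0.90 = 64% | 1.03 | 2 points |

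Assume further that 25% to 40% of participants have baseline HbA1c of at least 6.5%. The number per 100 randomized who qualify through an unrelated drug alone is 100 × share × p_new × (1 − p_true):
- Low end: 100 × 0.25 × 0.20 × 0.90 = 4.5.
- High end: 100 × 0.40 × 0.60 × 0.95 = 22.8.

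The last factor removes participants who also truly worsen. Without it the products are 5 and 24.

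**The case against.** The strongest reply is that no sensible reader would apply the text literally. The phrase defines glycaemic worsening and applies to people whose HbA1c is already raised. The criteria around it name their drug class. SAP Section 6 puts detailed programming specifications in a separate document, where a class filter may already exist. On intent this stands: antidiabetic medication is almost certainly what was meant. It does not repair the text, because a prespecified definition should not depend on the programmer supplying a missing word.

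A reader might infer that unrelated drugs will in fact be counted as glycaemic events. The documents do not show that. SAP Section 3.5.2 describes output for NODM only, and Protocol Section 8.1.4 says "These ESIs will be monitored through review of the AE and laboratory databases", without naming the medication data. On the other side, the medication part of the definition cannot be assessed without medication data, and ESI incidence is to be summarized. What is shown is that such drugs qualify under the definition, not that a table will include them.

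A reader might also infer that a real glycaemic difference would be hidden. That is not supported either. HbA1c and fasting glucose are in the chemistry panel and are summarized with change from baseline (SAP Section 3.5.3). NODM has its own criteria. Adverse events are tabulated by system organ class and preferred term, and concomitant medications by ATC class and arm. A real signal would still have these routes to show itself.

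Finally, the rates in the illustration are assumed. Type 2 diabetes is one qualifying risk factor and entry excludes only HbA1c of 10.0% or more (or fasting glucose of 270 mg/dL or more), but neither fact gives the share with baseline HbA1c of at least 6.5%. This objection stands in full.

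**Conclusion.** The point holds as a defect in the definition, at low severity. Read with the SAP's own meaning of concomitant medication, the first alternative admits any new drug in a participant with baseline HbA1c of at least 6.5%. The consequence is conditional: if the text is programmed literally, unrelated prescriptions qualify as glycaemic ESIs, the descriptive category is inflated, and any contrast between arms within it is diluted.

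The size cannot be derived from the documents. The illustration shows the direction of the effect and how it grows with the rate of new prescriptions. It is not an estimate for this trial, and it rests on independence and on rates chosen for the purpose. No hypothesis test, significance level, sample size or efficacy result is touched.

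**What to change.** In SAP Section 3.5.2 and Protocol Section 8.1.4, reword the medication part as *a new antidiabetic medication or an increase in current antidiabetic therapy*. In the SAP, state that the drugs are identified by the glucose-lowering ATC class from the coding under Section 3.3.6, and say whether and how worsening of glycemic control is to be tabulated.

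The cost is one qualifier in each document, one filter in the derivation and a sentence on output. No new data are needed, and visits and participant care do not change. It should be done before unblinding, since narrowing the drug class afterwards would be a post hoc change to a safety definition.
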